### 6.5.1 Study Time and Events Table

#### Phase One: Observational Study

Study Procedures	Day 1-8	Month 2	Month 5	Month 7
Study Interval	Screening/Enrollment	Active phase		
Informed consent	X			
Demographics	X			
Medical history	X			
Weight	X	X	X	X
Physical examination	X	X	X	X
Vital signs	X	X	X	X
Standard of care EHL questionnaire	X	X	X	X
Study questionnaires	X	X	X	X
WIC information		X	X	X

#### Phase Two: Randomized Controlled Trial

Study time table and events for Phase Two, Randomized Controlled Trial are the same as Phase One, Observational Study except: Day 1-8 Geisinger and WIC will verify that the participant is a Geisinger patient who provided informed consent to participate in the study and the infant is enrolled as a WIC participant. After the participant is authenticated as receiving care at both Geisinger and WIC, data sharing will be enabled between Geisinger and WIC. Bi-directional data sharing between Geisinger and WIC will continue for the 6 month intervention (last data collection point at 7 months).

### 6.5.2 Study Flow Diagram

Figure 6.5.2-1: Phase One Observational Study Flow Diagram

[figure not shown]
[figure not shown]

[figure not shown]
Figure 6.5.2-2: **Phase Two Randomized Controlled Trial Flow Diagram**

### Primary Endpoints

The primary endpoint will be excessive rapid weight gain, or weight-for-age z-scores, at post-intervention. The phase one observational study provides the naïve condition of weight-for-age z-scores that will be compared to treatment group in the randomized controlled trial. A 0.67 difference in weight-for-age z-scores represents the distance between major centile lines displayed on infant growth charts. This difference is clinically meaningful, and upward percentile crossing of this magnitude has been the operational definition for rapid weight gain.

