**Disease/Diagnosis:** Data from the National Health and Nutrition Examination Survey demonstrate the need for early intervention to prevent obesity: 1 in 10 infants and toddlers are obese with those from lower socio-economic (SES) households at greater risk than their higher-SES counterparts. Pennsylvania is 1 of 3 states to demonstrate significant increase in obesity rates among low-income preschoolers (aged 2-4 years) from 2008-2011. Further, Black/African American children showed divergence from white/Caucasian children in BMI growth trajectories by age 5 years even when controlling for known economic status, calling for greater attention to reduce health disparities. Excessive rapid weight gain during infancy also predicts obesity later in life, increasing the risk for health disparities. Thus, infancy is a sensitive period when parents can and should intervene to establish healthy patterns that may last a lifetime to combat the obesity epidemic. These issues provide strong justification for focusing efforts on obesity prevention in low-income and racial/ethnic minority group mother/guardian-infant dyads, starting in early life in Pennsylvania.

**Population to be Studied:** Mother/guardians of newborn Geisinger patients who are also WIC eligible or participants.

**Endpoints:** Process outcomes include consistent messaging, patient engagement and satisfaction, maternal knowledge, attitude, self-efficacy, and maternal and child behavior; the primary impact outcome is rate of infant weight gain.

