### 6.2 Study Population

#### 6.2.1 Approximate Number of Subjects

Approximately 715 Geisinger subjects will participate in this study, 15 mother/guardian-infant pairs will participate in the observational phase and a total of 350 mother/guardian-infant pairs will participate in the RCT phase. The study team has accounted for participant drop-out by planning to enroll 350 Geisinger subjects, recognizing that a to meet power calculations a total of 15 observational control dyads and 350 intervention/control dyads are needed. Mother/guardian-infant pairs of infants that have a Geisinger primary care provider in the Geisinger Pediatric Service Line and who participate or are eligible and plan to participate in WIC will be enrolled in a single phase of the study. Pregnant women who are eligible for or participate in WIC who also intend to have their newborn receive care from a Geisinger primary care provider in the Geisinger Pediatric Service Line will be enrolled in a single phase of the study.

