## Secondary Endpoints

Secondary endpoints include consistent messaging; attitudes, beliefs, and knowledge; self-efficacy; and measures identified as “individual characteristics,” “responsive parenting,” and “infant intake” in Figure 1 boxes.

**Footnote:** Infant growth measures include rapid weight gain measured by change in weight-for-age z-score.

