### **6.6.2 Statistical Power and Sample Size Considerations**

We have powered the study to detect a 0.67 difference in weight-for-age z-scores between the observational and future intervention groups. To detect this difference with 90% power and a 5% Type I error rate, 276 participants are required. This includes an anticipated 30% loss to dropout. This study is also powered on food to soothe a distressed child and uses nominal power = 0.8 and alpha = 0.05. If we assume that we can change 15% of mothers in the future treatment group to reduce their use of food to soothe as compared to mothers in the observational study, assume a constant variance of 1 and a retention rate of 67% during the study period, we will need to recruit 300 pediatric participants. We have experienced a 31-33% drop-out rate in previous studies of mother/guardian-infant dyads for longer than 3 months duration, and so assume a similar drop-out for this study.

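### The primary endpoint text and the power statement compare the treatment arm with the 15-dyad Phase 1 cohort, although the trial is randomised 1:1, and the growth outcome is stated in more than one form

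*Protocol*

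**What the plan says.** **Comparator.** The Primary Endpoints section describes Phase 1 as supplying naïve-condition z-scores "that will be compared to treatment group in the randomized controlled trial". Section 6.6.2 says the study is powered to "detect a 0.67 difference in weight-for-age z-scores between the observational and future intervention groups", and continues: "To detect this difference with 90% power and a 5% Type I error rate, 276 participants are required", with 30% dropout included. Its second calculation, on food to soothe, also compares treated mothers with those in the observational study. Section 6.2.1 gives the group sizes: "to meet power calculations a total of 15 observational control dyads and 350 intervention/control dyads are needed".

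The Abstract gives the purpose of the randomised trial as comparing coordinated with uncoordinated care, and section 6.1 randomises 1:1. Section 6.6.1 plans a linear mixed model of weight-for-age z-score by study group, without naming the groups.

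**Outcome.** The primary endpoint is worded "The primary endpoint will be excessive rapid weight gain, or weight-for-age z-scores, at post-intervention". The Endpoints paragraph of section 3 says "the primary impact outcome is rate of infant weight gain". The footnote under Secondary Endpoints says "Infant growth measures include rapid weight gain measured by change in weight-for-age z-score". The Primary Endpoints section adds, of 0.67 z, that "upward percentile crossing of this magnitude has been the operational definition for rapid weight gain".

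**The concern.** The passages that define the primary endpoint and justify the sample size point to a different pair of groups from the passages that define the trial. Nothing ranks the two contrasts, so a reader cannot tell which one carries the confirmatory result.

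The choice matters for two reasons. First, 15 comparators cannot support the stated 90% power unless the z-score SD is well below 1. Second, the Phase 1 contrast lacks the protection of randomisation. Phase 1 runs earlier. Section 6.2.2 limits only Phase 2 to Partners in Pediatrics and Luzerne County WIC. By the Abstract, EHL screening is switched off during Phase 1 and back on in Phase 2. A difference from Phase 1 could therefore not be credited to care coordination alone.

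The outcome wording adds a second ambiguity. Attained z-score and change in z-score are different quantities unless the analysis adjusts for the starting value.

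**Working it through.** **Inputs.** Difference 0.67, power 90%, type I error 5%, loss 30%, total 276 (section 6.6.2). 15 Phase 1 dyads and 350 randomised dyads (section 6.2.1), so 175 per arm at 1:1. After 30% loss: 175 × 0.70 = 122.5 and 15 × 0.70 = 10.5, taken as 122 and 10. Two assumptions are needed: a two-sided test, because sidedness is not stated, and the SD, because section 6.6.2 gives none for z-scores (its variance of 1 belongs to the food-to-soothe calculation). The SD is varied from 0.8 to 1.44.

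**Step 1: the plan's 276.** For two equal groups, n per group = 2 × (1.960 + 1.282)² × SD² / 0.67² = 46.8 × SD². Two routes lead to 276:

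- SD 1: 47 per group, or 48 by the t-test. Then 48 / 0.70 = 69 per group and 138 dyads in all. Counting mother and infant separately, 2 × 138 = 276. Section 6.2.1 counts in a similar way: its 715 subjects equal 15 + 2 × 350.
- Counting dyads: 276 × 0.70 / 2 = 96.6 per group, which implies SD = 0.67 × √(96.6 / 2) / 3.2415 = 1.44.

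The protocol does not say which route was used. Both need two equal groups, of 69 or 138 dyads each. Neither allows for 15 comparators.

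**Step 2: power of each contrast.** Noncentral t with n1 + n2 − 2 degrees of freedom and noncentrality 0.67 / (SD × √(1/n1 + 1/n2)). At SD 1:

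- 15 v 175: 0.67 / 0.269 = 2.49
- 10 v 122: 0.67 / 0.329 = 2.04
- 122 v 122: 0.67 / 0.128 = 5.23

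| Contrast | SD 0.8 | SD 1.0 | SD 1.44 |
|---|---|---|---|
| Phase 1 v treatment, no loss (15 v 175) | 87% | 70% | 41% |
| Phase 1 v treatment, 30% loss (10 v 122) | 71% | 52% | 29% |
| Randomised arms, 30% loss (122 v 122) | >99% | 99.9% | 95% |

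A larger treated group does not rescue the Phase 1 contrast. With 15 controls, SD 1 and unlimited treated infants, power is P(Z > 1.96 − 0.67 × √15) = 74%. Reaching 90% at SD 1 takes 28 evaluable Phase 1 infants against 175 treated, or 30 against 122.

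**Step 3: detectable difference at 90% power** (normal approximation, 3.2415 × SD × √(1/n1 + 1/n2)). At SD 1 this is 0.87 for 15 v 175, 1.07 for 10 v 122, and 0.42 for 122 v 122. At SD 1.44 the randomised arms detect 0.60.

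**Step 4: the outcome passages side by side.** Section 6.6.1 models the z-score and section 6.6.2 powers a difference in z-scores. Section 3 makes rate of gain primary, the footnote uses change in z-score, and the Primary Endpoints section couples rapid gain and z-score with a bare alternative. The unresolved choice is mainly attained z-score against change.

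**The case against.** The best defence is that the Primary Endpoints section only adds a comparison with Phase 1. It does not call that contrast sole or confirmatory, and the Abstract gives Phase 1 the purpose of a baseline. A reader might infer that the plan discards its randomised control arm. The documents do not go that far. What stands is narrower: section 6.6.2 attaches the 90% power to the Phase 1 contrast, and no section ranks it below the randomised one.

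A reader might also infer that a yes/no rapid-gain analysis is planned as primary, or that the outcome will be chosen after the data are seen and the 5% error rate lost. Neither is supported. The planned model and the power statement use the continuous z-score, 0.67 serves there as the size of a meaningful difference, and no passage permits a post hoc choice.

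The screening difference between phases is not a settled fact. The Abstract has EHL off in Phase 1, yet the Phase One table in section 6.5.1 lists the EHL questionnaire at all four time points. The Abstract exposes both Phase 2 groups to EHL, yet section 6.5 says it will not fire for control participants, who receive it by mail. These passages must be reconciled. Calendar time and catchment remain as differences in any case.

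Finally, section 6.5 takes weights from health records, so survey dropout need not lose them, and 10 v 122 is a lower case. Without any loss, the Phase 1 contrast still falls short of 90% throughout the SD range shown.

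**Conclusion.** The point holds and should be corrected before any comparative analysis. The protocol names two different comparators for its main growth result, ranks neither, and attaches its 90% power to the one that cannot deliver it. Across SD 0.8 to 1.44, the Phase 1 contrast has 87% to 41% power with no loss and 71% to 29% after 30% loss. The randomised contrast has at least 95% throughout. The randomised design is therefore large enough for 0.67; the fault lies in the stated comparison. The figures rest on the assumed SD and a two-sided test.

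The 276 is not shown to be wrong. It can be reached in two ways, but only with two equal groups. The outcome inconsistency is real but smaller, and is mainly attained z-score against change.

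**What to change.** - Make intervention versus control, as randomised, the primary contrast, using the mixed model already planned in section 6.6.1 and naming the groups in it.
- Name one continuous primary outcome with its time point, for example weight-for-age z-score at the 7-month collection point. State how post-intervention applies to infants enrolled late, since section 6.2.2 admits them up to 6 months of age and the intervention lasts 6 months.
- Adjust for birth z-score. With it as a covariate, attained z-score and change from birth give the same group difference, so the question of weight gain is still answered. Add an analysis without it, because birth follows randomisation for women enrolled in pregnancy.
- Make rapid weight gain (a rise above 0.67) secondary, and the Phase 1 comparison descriptive.
- Restate section 6.6.2 for the randomised contrast with its SD, sidedness, counting unit (dyads or individuals) and 30% loss. About 122 per arm detect roughly 0.42 z at SD 1, or 0.60 z at SD 1.44, with 90% power. The food-to-soothe calculation needs the same change of comparator.
- Reconcile the EHL statements in the Abstract, section 6.5 and section 6.5.1.

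The cost is a rewrite of the Primary Endpoints section and section 6.6.2, with matching outcome wording in section 3 and the footnote. The Phase 1 contrast loses any confirmatory status. No new visits or data are needed.

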## Secondary Endpoints

Secondary endpoints include consistent messaging; attitudes, beliefs, and knowledge; self-efficacy; and measures identified as “individual characteristics,” “responsive parenting,” and “infant intake” in Figure 1 boxes.

**Footnote:** Infant growth measures include rapid weight gain measured by change in weight-for-age z-score.

## 6.6 Statistics

The statistical analyses will be performed at the Pennsylvania State University by [name] and [name].

### 6.6.1 Statistical Analysis Plan

Subscales for survey instruments will be treated as parametric data, and repeated analysis of variance will be used to assess the effects of the future intervention on changes of these composite outcomes and changes in child growth. All models considered will include relevant time-varying and stable-covariates. Covariates to be considered in refining the analyses can be grouped into categories that include maternal biologic variables, socioeconomic and demographic variables, infant behavioral variables, and parental behavioral variables. A linear mixed-effects model, a generalization of regression, will be used to examine the relationship between weight-for-age z-score and study group. The moderating effect of maternal mental health and child temperament on intervention efficacy will be tested. Continuous secondary parental and infant behavior outcomes assessed at multiple time points, including sleep duration, feed duration, fussing and crying duration, feeding practices and attitudes and parenting sense of competence, will be analyzed using appropriate time series methods. These methods will allow us to create summary variables to identify patterns of change. These patterns will be predicted by

---

the effects of the model, namely study group, initial feeding mode intent, and their interaction. These secondary outcomes will be included as moderators in analyses of primary growth outcomes. The moderator hypothesis represents the interaction between these variables and the main effects of the model while including each of these variables as additional main effects. We will also test whether these secondary variables function as mediators; that is are these variables predicted by the effects of the model and, in turn, predict the primary outcomes. Using path modeling to test these models, we will be able to determine the direction of influence among the variables in the model.

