## 4 HYPOTHESIS AND SPECIFIC AIMS

### 4.1 Hypothesis

The project tests the hypothesis that an individually-tailored, responsive parenting obesity prevention intervention that coordinates care provided by WIC nutritionists and primary care providers will be more effective than usual care at 1) delivering consistent messages and 2) changing maternal and infant behavior to 3) reduce/prevent obesity in infants.

### 4.2 Specific Aim 1

Establish the efficacy of an individually-tailored behavioral intervention designed to prevent overweight at age 1 by providing coordinated, personalized care on responsive parenting across multiple settings.

### 4.3 Specific Aim 2

Conduct mediation analyses to improve understanding of how the intervention components, parent factors, and child behaviors influence rapid weight gain and to explain differential responses to our responsive parenting intervention that coordinates care across settings (WIC clinics, PCP).

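### The protocol names two different primary comparisons, one resting on 15 non-randomised dyads, and its covariate rule lets post-randomisation behaviours into the weight-for-age model

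*Protocol*

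**What the plan says.** **Comparison.** Section 2 gives the purpose of the RCT phase as comparing coordinated with uncoordinated care, and section 6.1 randomises that phase 1:1. The Primary Endpoints text (under 6.5.2) says that weight-for-age z-scores from the phase-one observational study will be compared with the treatment group of the RCT. Section 6.6.2 powers the study for a 0.67 difference between the observational and intervention groups. Its second calculation, on food to soothe, also takes the observational mothers as comparator. Section 6.2.1 plans 15 observational dyads and 350 RCT dyads, and says these numbers meet the power calculations. The mixed model in 6.6.1 relates weight-for-age z-score to study group without saying which groups are meant.

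**Covariates.** Section 6.6.1 states "All models considered will include relevant time-varying and stable-covariates". The list headed "Covariates to be considered in refining the analyses" ends with "infant behavioral variables, and parental behavioral variables". Section 4.1 expects the intervention to work by "changing maternal and infant behavior to 3) reduce/prevent obesity in infants".

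**Moderators and mediators.** In 6.6.1 the repeatedly measured behaviour outcomes are summarised as patterns of change and predicted by "the effects of the model, namely study group, initial feeding mode intent, and their interaction". The section continues "These secondary outcomes will be included as moderators in analyses of primary growth outcomes", entering the interactions "while including each of these variables as additional main effects", and then "We will also test whether these secondary variables function as mediators".

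**The concern.** An analyst who follows the Primary Endpoints text and 6.6.2 would rest the efficacy conclusion on a comparison that is not randomised. It also differs in calendar time and in exposure to the revised screening tool, and has 15 dyads on one side. An analyst who follows sections 2 and 6.1 would use the randomised arms. Both could claim to be following the protocol.

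The covariate rule raises a separate problem. Follow-up behaviours are measured after randomisation, and on the trial's own hypothesis they lie between group and weight. If they enter the weight-for-age model, part of the effect passing through behaviour is removed. Where behaviour and weight share causes, some confounding is added. The result is not the effect of being randomised to coordinated care.

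**Working it through.** **1. The plan's 276.** Section 6.6.2 gives difference 0.67, power 90%, type I error 5% and 30% dropout. It gives no SD for the z-score and does not say whether the test is two-sided. A two-sided test is assumed.
- SD 1, two-sample t-test: 48 per group. 48/0.70 = 68.6, so 69 recruited per group, or 138 dyads. 2 × 138 = 276, an exact match if mother and infant are both counted. Section 6.2.1 counts RCT subjects that way: 15 + 2 × 350 = 715.
- If 276 means dyads: 276 × 0.70/2 = 96.6 per group, and the implied SD is 0.67/[(1.960 + 1.282) × √(2/96.6)] = 1.44.

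Both readings need two equal groups. Neither describes a comparison with 15 dyads on one side.

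**2. Power for 0.67 under each comparison.** The 350 RCT dyads at 1:1 give 175 per arm. Retention is 70% or 67%, the two figures in 6.6.2. SE = SD × √(1/n₁ + 1/n₂); two-sided 5% t-test.

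| Comparison (n analysed) | SD | SE | 0.67/SE | Power |
|---|---|---|---|---|
| Observational 15 v treatment 175, no dropout | 1 | 0.269 | 2.49 | 70% |
| 10.5 v 122.5 (30% dropout) | 1 | 0.322 | 2.08 | 54% |
| 10 v 117 (33% dropout) | 1 | 0.330 | 2.03 | 52% |
| Randomised 117 v 117 | 1 | 0.131 | 5.12 | above 99% |
| 10 v 117 | 1.44 | 0.474 | 1.41 | 29% |
| Randomised 117 v 117 | 1.44 | 0.188 | 3.56 | 94% |

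A larger treatment group does not help. At SD 1 with 10.5 observational dyads retained, power cannot exceed Φ(0.67 × √10.5 − 1.96) = 58%.

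**3. Adjusting for a post-randomisation behaviour.** The documents give none of the inputs, so this is an illustration. Take one behaviour, coded so that higher is better, with within-arm SD 1. The group effect on it is a = 0.40 SD, its within-arm correlation with weight is ρ = 0.1 to 0.3 in absolute value, and the weight SD is s = 1. The adjusted group difference is the total minus ρ × s × a:
- ρ = 0.1: 0.67 − 0.04 = 0.63
- ρ = 0.2: 0.67 − 0.08 = 0.59
- ρ = 0.3: 0.67 − 0.12 = 0.55

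With a = 0.2 the range is 0.65-0.61, and with a = 0.8 it is 0.59-0.43. If a or ρ is zero there is no distortion.

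**The case against.** **Both comparisons could be run.** Section 2 states the purpose of the RCT phase, and the Primary Endpoints text might only add an observational benchmark. That is fair as far as it goes. But the benchmark sits in the primary endpoint definition, and 6.6.2 powers nothing else, so the conflict remains.

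**The covariate wording is soft.** Relevance and consideration leave room for choice, covariate selection is often left to a separate analysis plan, and some behaviour values may be baseline. This reduces the point but does not remove it. The sentence covers every model and expressly admits time-varying covariates, and behaviour is a named category.

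**A stronger reading to resist.** A reader might infer that the moderator sentences put post-randomisation behaviours into the primary model and let its group coefficient decide efficacy. The text does not say so. The mixed-model sentence lists no behaviour variable, and the moderator sentences come later and target an interaction, for which main effects are routine. Section 4.3 already plans mediation analysis.

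**Larger consequences to resist.** A reader might also infer a serious loss of power or an inflated type I error. Loss of power below 90% under the a = 0.40 illustration appears only at SD 1.44, which rests on reading 276 as dyads, whereas SD 1 reproduces 276 exactly. At SD 1, power after adjustment stays at about 99% for a = 0.40. Type I inflation would require the group to change behaviour with no total effect on weight, which is not the trial's hypothesis.

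**Conclusion.** The point holds as two claims of different weight.

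The main one is the contradiction over the primary comparison. As written in the Primary Endpoints text and 6.6.2, the comparison is non-randomised and falls well short of 90% power: about 52-54% after dropout, or 70% with complete retention. Those figures assume SD 1, which is not stated. At SD 1.44 the figure after 33% dropout is 29%. The randomised comparison gives above 99% and 94% respectively, so the planned RCT is large enough and only the text points elsewhere.

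The second claim is narrower: the covariate rule does not keep post-randomisation behaviours out of the weight-for-age model. That adjustment changes what is estimated follows from the protocol's own hypothesis. How much it changes cannot be derived from the documents, and 0.63-0.55 for a true 0.67 is illustrative. The moderator and mediator models are sound as supplementary work.

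**What to change.** - In 6.6.1, define study group for the primary analysis as the two randomised arms. Limit covariates in that model to those measured before randomisation or that randomisation cannot affect.
- Reconcile the Primary Endpoints text and 6.6.2 with this. Present any comparison with the observational group as secondary and non-randomised. Restate the power for the randomised comparison, giving the SD and saying whether the count is dyads or individuals.
- State that group coefficients from models containing post-randomisation behaviours are not used for the efficacy conclusion.
- Use one form of the growth outcome throughout. The Endpoints paragraph of section 3 has rate of gain, the Primary Endpoints text a post-intervention z-score, and the footnote under Secondary Endpoints a change in z-score.

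The cost is wording: no new data, no extra participants, and no planned moderator or mediator analysis is dropped. Some freedom in covariate choice is lost, and one check is needed. Section 6.5 randomises after consent, but the phase-one procedures that it carries over allow an unfinished enrolment packet to come back within a week. On the remote route, enrolment follows return of both the consent and the completed survey. The sponsor should confirm which enrolment items precede group assignment on each route.

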## 6 STUDY DESIGN

### 6.1 Description

This prospective study will have two sequential phases 1) observational study; 2) interventional randomized controlled trial. In phase 2, qualifying participants will be randomized 1:1 to receive either Treatment A or Treatment B.

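### Section 6.6.1 says path modelling will determine the direction of influence; direction between behaviours and infant growth is assumed by these models, not tested

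*Protocol*

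**What the plan says.** Specific Aim 2 (Section 4.3) is "Conduct mediation analyses to improve understanding of how the intervention components, parent factors, and child behaviors influence rapid weight gain". Section 6.6.1 gives the method. Repeatedly measured behaviours are first reduced: "These methods will allow us to create summary variables to identify patterns of change". Those patterns are then predicted by the model effects, "namely study group, initial feeding mode intent, and their interaction". The secondary variables are examined as moderators of growth and also as mediators, the mediator question being "are these variables predicted by the effects of the model and, in turn, predict the primary outcomes". The section ends: "Using path modeling to test these models, we will be able to determine the direction of influence among the variables in the model".

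On design, Section 6.1 states that "qualifying participants will be randomized 1:1 to receive either Treatment A or Treatment B". Nothing else in the protocol qualifies the sentence on direction.

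**The concern.** The sentence credits path modelling with a property it lacks. Randomisation fixes the direction of the arrows that leave study group. It does not fix the arrow from behaviour to growth, which is the one Aim 2 is about. Reverse influence is plausible for the behaviours listed: feed duration, crying and feeding practices may respond to an infant's appetite or growth as well as shape it.

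At stake is what Aim 2 may conclude. Under the present wording, an arrow that the analyst drew could be reported as one that the data established, and could then inform which parts of the intervention are thought to work.

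**Working it through.** The plan gives no figure to reproduce. The check is whether fit can distinguish the two orderings.

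**Inputs from the protocol.** Exogenous effects P: study group X, feeding-mode intent F and their interaction XF (Section 6.6.1). Mediator M: a secondary behaviour. Outcome Y: growth. Sample sizes, used only for scale: "a total of 350 mother/guardian-infant pairs will participate in the RCT phase" (Section 6.2.1) and "a retention rate of 67% during the study period" (Section 6.6.2), giving 350 × 0.67 = 234.5, about 235.

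**Step 1: parameter count with direct paths kept.** The five variables X, F, XF, M, Y have 5 × 6 / 2 = 15 variances and covariances. Six belong to the three exogenous terms. Forward model: M on P has 3 coefficients and 1 residual variance; Y on M and P has 4 coefficients and 1 residual variance. Total 6 + 4 + 5 = 15, so df = 0. Exchanging M and Y gives the same count, so df = 0 again.

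**Step 2: likelihood.** The two models factor the same joint distribution:

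f(M | P) × f(Y | M, P) = f(M, Y | P) = f(Y | P) × f(M | Y, P).

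Under Gaussian maximum likelihood the maximised values are therefore identical in any data set of any size.

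**Step 3: numerical check.** Data were simulated under three truths, with assumed effect sizes, residual SD 1 and U an unmeasured cause:

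- behaviour drives growth: M = 0.4X + 0.2F + e, Y = 0.4M + e;
- growth drives behaviour: Y = 0.4X + 0.2F + e, M = 0.4Y + e;
- confounding only: M = 0.4X + 0.2F + 0.6U + e, Y = 0.6U + e.

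There were 2,000 runs at n = 350 and at n = 235, and 5 runs at n = 100,000. With direct paths kept, the forward and reversed log-likelihoods differed by less than 5 × 10⁻¹³ at the two trial sizes and by at most about 1.2 × 10⁻¹⁰ at 100,000. That is rounding error.

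**Step 4: direct paths removed (full mediation).** Each model now omits three direct paths, so fit can differ. Share of runs in which fit preferred M → Y:

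| Truth | n = 350 | n = 235 |
|---|---|---|
| M → Y | 98.1% | 95.2% |
| Y → M | 1.8% | 6.1% |
| No M–Y effect, shared cause only | 97.3% | 92.8% |

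The Monte Carlo standard error is at most √(0.928 × 0.072 / 2,000) = 0.6 percentage points.

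The first two rows show that fit finds the direction when there is no direct effect and no confounding. The third shows what happens when confounding is present. There both restricted models are wrong and fit picks the less wrong one. Given P, cov(M, Y) = 0.6² = 0.36 and var(M) = 0.36 + 1 = 1.36, so the forward model omits a group coefficient of −0.4 × 0.36 / 1.36 = −0.106 on Y, while the reversed model omits one of 0.4 on M. The preference for M → Y comes from group acting on M, not from M acting on Y.

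**The case against.** The strongest reply is that Steps 1 and 2 cover one mediator-outcome triple with direct paths, a model the protocol does not specify. The schedule in Section 6.5.1 has questionnaires and weights at enrolment and at months 2, 5 and 7. In a repeated-measures path model, earlier behaviour to later weight and earlier weight to later behaviour are separate, estimable paths. This stands as a limit. A reader might infer that the data carry no information on direction at any sample size; that is exact only with direct paths kept. What lagged or full-mediation models add still depends on time order, absence of confounding or absence of a direct effect, none of which they test.

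A reader might also infer that mediator and outcome are measured concurrently. The protocol does not say so. The primary endpoint is placed after the intervention, and the mediator question is worded as a sequence. Equally, no lag is stated, and summary patterns of change may overlap the growth period.

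The choice of visit, the lag and any sensitivity analysis may sit in a statistical analysis plan that is not at hand, and an assumed ordering may be drawn in a figure that is not shown. Their absence from this text is therefore not the fault. Section 6.6.1 also plans time-varying and stable covariates, which helps with confounding but does not settle direction. What remains is an affirmative statement about a method, which further detail elsewhere would not make true.

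**Conclusion.** The sentence is wrong as written and should be changed. For the mediation model with direct paths kept, the result is exact and needs no assumed effect sizes: 0 degrees of freedom both ways and equal likelihood. For full mediation, the 97% and 93% figures illustrate how fit can point to a causal arrow that does not exist; their size depends on the effects chosen, including a shared-cause coefficient of 0.6. Lagged models were not simulated. The point about them is that they rely on a correct time order and no unmeasured mediator-outcome confounding.

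The consequence is confined to the interpretation of Aim 2. The randomised group comparison, the sample size and data collection are not touched.

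**What to change.** Replace the last sentence of the mediation paragraph in Section 6.6.1 with:

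> Path models will estimate indirect effects under a pre-specified, assumed causal order; direction is not tested. Mediators will be taken from visits before the 7-month weight outcome where available, adjusting for birth weight z-score and baseline maternal covariates, with a sensitivity analysis for unmeasured mediator-outcome confounding.

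Growth after randomisation should not be added as an ordinary regression covariate. It may already reflect the intervention, so adjusting for it can remove part of the effect to be explained, and it is a treatment-affected confounder that standard mediation adjustment does not handle. If it is included, a method suited to such confounders is needed. For dyads enrolled in pregnancy, birth weight may itself follow randomisation; adjusting for it then assumes that the intervention does not act before birth.

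The cost is one sentence and one sensitivity analysis on data already scheduled. Lagged mediators lose some precision. Because Section 6.2.2 allows enrolment up to 6 months of age, late-enrolled infants may lack an earlier mediator taken after randomisation, and the text should say how they are handled. If only a minimal change is wanted, saying that effects are estimated under an assumed causal order removes the error.
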